5.6.5 Electrocardiograms

Each parameter of ECG assessments (heart rate, QT interval, QTcB interval, QTcF interval, RR interval) will be summarized by visit based on actual value observed and its change from Baseline.

ECG findings (normal; abnormal, not clinically significant [NCS]; abnormal, clinically significant [CS]) will also be summarized as shift from Baseline to the worst value during the treatment period. In addition, the number (percentage) of subjects with at least 1 postbaseline abnormal ECG result in QTc, using both Bazett's (QTcB) and Fridericia's (QTcF) correction formulas, during the treatment period will be summarized. Clinically abnormal ECG results in QTcB and QTcF will be categorized as follows:

- Absolute QTc interval prolongation:
 - ≤ 450 ms
 - >450 ms - ≤ 480 ms
 - >480 ms - ≤ 500 ms
 - >500 ms
- Increase from Baseline in QTc interval:
 - ≤ 30 ms
 - >30 ms - ≤ 60
 - >60 ms

5.6.6 Other Safety Analyses

Shift tables for ECOG PS from Baseline to worst postbaseline score (0 to 4) will be presented.

Descriptive statistics for LVEF as assessed by either echocardiogram or MUGA and changes from Baseline will be summarized.

5.7 Other Analyses

Health-related Quality of Life will be described in a separate SAP.

5.8 Exploratory Analyses

Exploratory analyses may be conducted as appropriate. Any exploratory analyses that are performed will be appropriately titled and labeled as exploratory and will be clearly distinguished from planned analyses when results are reported in the Clinical Study Report.

6 INTERIM ANALYSES

No interim analysis is planned for this study.

7 CHANGES IN THE PLANNED ANALYSES

This SAP focuses on the analyses for the 2-arm design of the study.

The Safety Analysis Set will be used for the summary table of biomarker parameters, while the Pharmacodynamic Analysis Set will be defined in a separate SAP for PK/PD analyses.

The exploratory endpoint of Duration of Clinical Benefit will not be analyzed in this study as it is not a widely used and well-defined endpoint; furthermore, it was not included in the RR-DTC Phase 3 study, E7080-G000-303.

Clinically abnormal ECG results based on QTcB and QTcF will be summarized the same way as done in Study E7080-G000-303. The categories are slightly different than the ones stated in the study protocol.

8 DEFINITIONS AND CONVENTIONS FOR DATA HANDLING

8.1 Baseline

Baseline is defined as the nonmissing value most recently collected prior to the first dose of study drug.

8.2 Study Day

Study Day is defined as the day counting from the first lenvatinib dose date as follows:

- For a date on or after the first dosing date, Study Day= event date – first dose date of study drug +1
- For a date prior to the first dosing date, Study Day= event date – first dose date of study drug

8.3 Conversion Rules for Day to Month to Year

1 month = 30.4375 days; 1 year = 365.25 days.

8.4 Censoring Rules

The censoring rules for PFS are explained in [Table 4](#), based upon investigator's tumor assessments and the FDA Guidance for Industry, *Clinical Trial Endpoints for the Approval of Cancer Drugs and Biologics* (2007).

For PFS2, if a subject did not have PD (solely based on the investigator-provided information on the Survival Status eCRF) after starting a new anticancer treatment, or did not die during the study, the subject will be censored on the date last known to be alive.

For OS, in the absence of confirmation of death, subjects will be censored either at the date last known to be alive or the date of data cutoff, whichever is earlier.

Table 4 Censoring Rules for Progression-Free Survival

No.	Situation	Date of Progression or Censoring	Outcome
1	No baseline or postbaseline tumor assessments	Date of randomization	Censored
2	Progression documented between scheduled visits	Date of first radiologic PD assessment	Progressed
3	No progression at the time of data cutoff	Date of last adequate radiologic assessment prior to or on date of data cutoff	Censored
4	New anticancer treatment started	Date of last adequate radiologic assessment prior to or on date of new anticancer treatment	Censored
5	Death before first PD assessment	Date of death	Progressed
6	Death between adequate assessment visits*	Date of death	Progressed
7	Death or progression after more than one missed visit** or after 28 days from the last dose of study treatment	Date of last adequate radiologic assessment before missed tumor assessments	Censored
8	Treatment discontinuation for reasons other than PD	Date of last radiologic assessment before treatment discontinuation	Censored

CR = complete response, PD = progressive disease, PR = partial response, SD = stable disease.

* Adequate tumor assessment is a radiologic assessment of CR, PR, SD, non-CR/non-PD or PD as determined by investigators.

** More than 1 missed visits is defined as having either 1 of the following 2 durations being longer than 18 weeks - 1 day, which is 125 days ($= ((8+1) \times 2 \times 7) - 1$) for subjects on the every-8-week tumor assessment schedule in this study:

- a. Duration between 2 consecutive tumor assessments
- b. Duration between the last adequate tumor assessment and death or PD

The priority of the censoring rules is as follows:

1. If the subject had PD or death, the following sequence will be applied:
 - If a subject did not have a baseline tumor assessment (No. 1), the subject will be censored on the date of randomization. However, if the subject died within 125 days (18 weeks – 1 day) after randomization and did not receive new anticancer treatment, the date of death will be the PFS event date (not censored).
 - If a subject had new anticancer treatment before PD or death (No. 4), the subject will be censored on the date of the last tumor assessment prior to or on the start date of new anticancer treatment.
 - If PD is reported after the drug discontinuation visit, the subject will be censored at the date of last radiologic assessment before drug discontinuation except when PD occurred at the same visit as drug discontinuation (No. 8). If PD occurred within 4 weeks of drug discontinuation, it will be considered PD at the drug discontinuation visit and counted as a PFS event.
 - If a subject missed more than 1 assessment before PD or death (No. 7), the subject will be censored on the date of the last tumor assessment before PD or death. Note that if a subject is censored by both this criterion and the anticancer treatment criteria, the earliest censoring date will be used.
 - Otherwise, if a subject had an event (No. 2, No. 5 or No. 6), the earliest event date will be used.
2. If a subject did not have PD or death, the censoring date will be the earliest censoring date if the subject met multiple censoring criteria (No. 1, No. 3, No. 4, or No. 7).

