#### 9.5.1.2.2 SECONDARY EFFICACY ASSESSMENTS

The secondary efficacy endpoint is PFS defined as the time from the date of randomization to the date of first documentation of disease progression, or date of death, whichever occurs first. PFS censoring rules will be defined in the statistical analysis plan (SAP).

The date of the first subsequent objective disease progression on an anticancer therapy after objective progression on lenvatinib treatment will be collected (unless this information is not allowed to be provided due to confidentiality) and PFS2 will be calculated.

PFS2 is defined as the time from randomization to second objective PD (occurring during treatment with next line of anticancer therapy) or death from any cause, whichever occurs first. Censoring rules for PFS2 will be defined in the SAP.

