#### 9.7.1.1.2 SECONDARY ENDPOINTS

- PFS, defined as the time from the date of randomization to the date of first documentation of disease progression, or date of death, whichever occurs first. Censoring rules for PFS will be defined in the SAP and will follow FDA guidance.
- PFS2, defined as the time from randomization to second objective disease progression (occurring during treatment with next line of anticancer therapy), or death from any cause, whichever occurs first. Censoring rules for PFS2 will be defined in the SAP.
- Overall safety profile and tolerability.
- Time to treatment discontinuation due to an AE.
- Number of dose reductions.
- Time to first dose reduction.
- Plasma PK lenvatinib exposure parameters.
- Interrelationships of lenvatinib exposure, changes in thyroglobulin, TSH, or other exploratory serum biomarkers, and changes in tumor burden and PFS.
- Relationship of lenvatinib exposure and changes in BP, and AEs of weight loss, fatigue, nausea, vomiting, diarrhea, and proteinuria CTCAE grades derived from urine protein measurements.
- Impact of lenvatinib treatment on HRQoL as assessed using the validated instruments EQ-5D-3L and FACT-G.

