#### 9.7.1.6.2 SECONDARY EFFICACY ANALYSES

The stratified log-rank test using ECOG PS and age group as strata will be used to compare differences in PFS and PFS2 as assessed by investigator between the 24-mg and 18-mg treatment groups. The hazard ratio (HR) for the corresponding treatment comparisons will be estimated by the stratified Cox regression including treatment as a factor and baseline ECOG PS and age group as strata. The estimated HR will be reported for the treatment comparison between 24 mg vs 18 mg, along with the corresponding (2-sided) 95% CI. The Kaplan-Meier (KM) product-limit estimates for each treatment group will be reported and plotted over time.

PFS2 is defined as the time from randomization to second objective disease progression, or death from any cause, whichever occurs first. Subjects who are alive and for whom a second objective disease progression has not been observed will be censored at the last time they are known to be alive and without a second objective disease progression. Subjects who were enrolled prior to implementation of Amendment 03 and who discontinued lenvatinib treatment due to progressive disease or due to an AE were followed for PFS2 until the date that the last subject transitioned to lenvatinib treatment outside the study (the data cutoff date for this group of 41 subjects). PFS2 data for these subjects will be included in a separate report.

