5.1.2 Secondary Endpoints

- PFS, defined as the time from the date of randomization to the date of first documentation of disease progression, or date of death, whichever occurs first
- PFS2, defined as the time from randomization to second objective disease progression (occurring during treatment with next line of anticancer therapy), or death from any cause, whichever occurs first
- Overall safety profile and tolerability
- Time to treatment discontinuation due to an adverse event (AE)
- Number of dose reductions

- Time to first dose reduction
 - *Plasma PK lenvatinib exposure parameters
 - *Interrelationships of lenvatinib exposure, changes in thyroglobulin, TSH, or other exploratory serum biomarkers, and changes in tumor burden and PFS
 - *Relationship of lenvatinib exposure and changes in blood pressure (BP), and AEs of weight loss, fatigue, nausea, vomiting, diarrhea, and proteinuria CTCAE grades derived from urine protein measurements
 - *Impact of lenvatinib treatment on HRQoL as assessed using the validated instruments EQ-5D-3L and FACT-G
- * Will be provided in separate reports.

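### SAP 8.4 joins its two PFS2 censoring conditions with *or*, which contradicts the endpoint definition, and it does not require the progression to be a second objective one

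*SAP*

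**What the plan says.** SAP 5.1.2 defines PFS2 as the "time from randomization to second objective disease progression (occurring during treatment with next line of anticancer therapy), or death from any cause", with the earlier of the two taken. Protocol 9.7.1.1.2 gives the same definition and adds "Censoring rules for PFS2 will be defined in the SAP". Protocol 9.5.1.2.2 describes the progression date to be collected as the "first subsequent objective disease progression on an anticancer therapy after objective progression on lenvatinib treatment".

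Protocol 9.7.1.6.2 also states a censoring rule: "Subjects who are alive and for whom a second objective disease progression has not been observed will be censored". The date it gives is the last time they are known to be both alive and free of a second PD.

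SAP 5.4.2 repeats the whole PFS analysis for PFS2: stratified log-rank test at alpha 0.05, stratified Cox model and Kaplan-Meier estimates. For censoring it points to SAP 8.4. There, for a subject who had no PD according to the Survival Status eCRF, the rule continues "after starting a new anticancer treatment, or did not die during the study, the subject will be censored", at the date last known alive. SAP 7, which lists departures from the protocol, names none for PFS2.

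**The concern.** For an endpoint of the form *A or B, whichever comes first*, the only valid reason to censor is that neither A nor B was observed. SAP 8.4 repeats the negative on both sides of *or*, so the absence of either one triggers censoring. Two kinds of true event are lost: the living subject with a documented second PD, and the subject who dies without PD on a next line.

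The wording also drops the requirements that the PD be objective and be the second. Subjects may stop lenvatinib and start another therapy before any PD (protocol 9.3.3 and 9.5.4), so the PD that follows the new therapy can be their first.

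At stake are the event count, the hazard ratio and the survival curves of a named secondary endpoint.

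**Working it through.** The plan states no expected number of PFS2 events, no PFS2 power and no death rate, so there is no figure of its own to reproduce. The check is one of logic, followed by an illustration.

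**Step 1: the rules as logic.** Let F = PD before any new therapy, N = new therapy started, P = PD after new therapy, D = death.

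- Definition (SAP 5.1.2): event = (F and P) or D.
- SAP 8.4 as written: censored = (not P) or (not D), so event = P and D.
- SAP 8.4 with *and*: censored = (not P) and (not D), so event = P or D.

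**Step 2: all patterns.** Four yes/no facts give 16 patterns. Four of them (P without N) are impossible, which leaves 12.

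| F | N | P | D | Definition | 8.4 as written | 8.4 with *and* |
|---|---|---|---|---|---|---|
| no | no | no | no | censored | censored | censored |
| no | no | no | yes | event | **censored** | event |
| no | yes | no | no | censored | censored | censored |
| no | yes | no | yes | event | **censored** | event |
| no | yes | yes | no | censored | censored | **event** |
| no | yes | yes | yes | event | event | event |
| yes | no | no | no | censored | censored | censored |
| yes | no | no | yes | event | **censored** | event |
| yes | yes | no | no | censored | censored | censored |
| yes | yes | no | yes | event | **censored** | event |
| yes | yes | yes | no | event | **censored** | event |
| yes | yes | yes | yes | event | event | event |

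As written, 5 of 12 patterns disagree with the definition, and each is an event turned into a censoring. With *and*, 1 of 12 disagrees: no earlier PD, new therapy, first PD afterwards, alive. If that subject also dies, the status is right but the event could be dated at the first PD instead of at death.

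**Step 3: dates.** The protocol's date is when subjects were last "censored at the last time they are known to be alive and without a second objective disease progression"; the SAP's is the date last known alive. Table 7 footnote v of the protocol allows follow-up by telephone or email and lets PFS2 information be withheld for confidentiality, so a subject can be known alive with unknown progression status. The SAP then credits PFS2 time that was not assessed. Under the literal rule, a living subject with second PD is censored on or after the observed event. Unlike the OS rule in the same section, the PFS2 rule sets no limit at data cutoff.

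**Step 4: illustration with assumed rates (none are in the documents).** Let p = probability of second PD by cutoff, d1 = probability of death given second PD, d0 = probability of death without it. For simplicity, every PD after new therapy is taken as a second PD. With 152 subjects:

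- Events by definition = 152 × [p + (1 − p) × d0]
- Events under the literal rule = 152 × p × d1

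| p | d1 | d0 | Definition | Literal | Kept |
|---|---|---|---|---|---|
| 0.1 | 0.3 | 0.10 | 152 × 0.19 = 28.9 | 152 × 0.03 = 4.6 | 16% |
| 0.2 | 0.5 | 0.15 | 152 × 0.32 = 48.6 | 152 × 0.10 = 15.2 | 31% |
| 0.3 | 0.6 | 0.20 | 152 × 0.44 = 66.9 | 152 × 0.18 = 27.4 | 41% |

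The share kept, p × d1 / [p + (1 − p) × d0], rises with p and d1 and falls with d0. Recombining the same values, the worst case is p = 0.1, d1 = 0.3, d0 = 0.20: 0.03 / 0.28 = 11%. The best is p = 0.3, d1 = 0.6, d0 = 0.10: 0.18 / 0.37 = 49%. The share can never exceed d1, because the denominator is at least p.

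**The case against.** The strongest reply is that this is a one-word slip that nobody would program. SAP 5.1.2 and protocol 9.7.1.6.2 both carry the right logic, and SAP 7 declares no change. The literal rule is also odd on its face, since it would censor a subject with a known death date at the date last known alive. The PFS rules in the same section use a joint negative to mean neither event. A careful programmer would probably follow the definition. All of this stands, and it makes *and* the likely intention. It does not cure the text: the protocol defers PFS2 censoring to the SAP, and SAP 5.4.2 refers to 8.4.

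A second reply is that 8.4 states only who is censored, and what counts as an event stays in 5.1.2, which requires a second objective PD. This also stands in part: that a first PD after new therapy would count is an inference from 8.4, not something it states. Protocol 9.4.5.2 treats additional antitumor therapy as evidence of progression, but that is not an objective PD, and SAP Table 4 censors such subjects for PFS.

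A reader might infer more than the documents support:

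- That both defects act at full strength together. They do not. Under *or*, a PD after new therapy counts only if the subject also died; under *and*, the loss of events disappears.
- That the trial will in fact lose most of its PFS2 events. That requires the literal rule to be programmed, and it depends on death rates the documents do not give.
- That first progressions counted as second ones fall mainly in subjects who stopped for toxicity and so favor one dose. This is plausible, but no figure supports it.

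**Conclusion.** Wrong as written. The literal rule in SAP 8.4 contradicts SAP 5.1.2 and protocol 9.7.1.6.2 in 5 of 12 outcome patterns. Changing *or* to *and* leaves one mismatch in event status, plus the looser censoring date.

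The logical result needs no assumption. The size does: over the assumed rates above, the literal rule keeps 11% to 49% of PFS2 events. It could keep more than half only if most subjects with a second PD had died by cutoff and few others had.

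PFS2 is a secondary endpoint with no stated power. The noninferiority test on response at 24 weeks and the sample size of 152 are unaffected.

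**What to change.** Replace the PFS2 paragraph in SAP 8.4 with text to this effect:

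> A PFS2 event is the earlier of death from any cause and second objective PD. Second objective PD means PD during next-line anticancer therapy that follows a documented first objective PD, whether that first PD was found on or after study treatment. A subject who is alive with no second objective PD is censored at the last date known to be both alive and free of second objective PD, and no later than the data cutoff. A first PD that occurs after a new therapy was started without earlier PD is not by itself a PFS2 event.

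The first PD should not be restricted to PD while on study drug. Subjects who stop without PD continue to be scanned (protocol 9.3.3, 9.5.4 and Table 7 footnote r), and such a restriction would discard second progressions in those whose first PD was found off treatment.

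The cost is a few sentences in the SAP and one derivation: first PD from the tumor assessments, second PD from the Survival Status eCRF. The protocol already provides for collecting the second progression date, so no new data should be needed, although the eCRF is not among the documents and should be checked. The change belongs before database lock and unblinding.

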#### **Analysis of Secondary Endpoints:**

Progression-free survival and PFS2 will be analyzed using stratified Cox regression including treatment as a factor and baseline ECOG PS and age group as strata. The estimated hazard ratio (HR) will be reported for the treatment comparison between the 24-mg and 18- mg dose groups along with the corresponding 95% CIs. The Kaplan-Meier (KM) product-limit estimates for each treatment group will be reported and plotted over time.

PFS2 is defined as the time from randomization to second objective disease progression (PD) or death from any cause, whichever occurs first. Subjects who are alive and for whom a second objective PD has not been observed will be censored at the last time they are known to be alive and without a second objective PD. Subjects who were enrolled prior to implementation of Amendment 03 and who discontinued lenvatinib treatment due to progressive disease or due to an AE were followed for PFS2 until the date that the last subject transitioned to lenvatinib treatment outside the study (the data cutoff date for this group of 41 subjects). PFS2 data for these subjects will be included in a separate report.

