The Treatment Period for an individual subject will begin at the time of randomization and will end upon completion of the Off-treatment Visit, which will occur within 30 days after the final administration of study drug. Serious adverse events (SAEs) must be captured for 28 days after the last dose of study drug. Subjects will undergo safety and efficacy assessments as defined in the Schedule of Procedures and Assessments (Table 7) and will continue to receive study treatment until disease progression. The Follow-up Period will begin immediately after the Off-treatment Visit and will continue as long as the subject is alive unless the subject withdraws consent, or until the data cutoff for primary analysis. Subjects who discontinue study drug treatment prior to disease progression will continue to be followed according to the Schedule of Procedures and Assessments until documentation of disease progression or initiation of another anticancer treatment. Subjects will be followed every 12 weeks  $\pm$  1 week for survival, PFS2 and all anticancer treatments received (unless this information is not allowed to be provided due to confidentiality) will be recorded until the data cutoff for primary analysis. Subjects who were enrolled prior to implementation of Amendment 03 and who discontinued lenvatinib treatment due to progressive disease or due to an AE were followed for PFS2 and survival until the date that the last subject transitioned to lenvatinib treatment outside the study (the data cutoff date for this group of 41 subjects).

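### SAP Section 8.4 drops the protocol's progression-status condition from PFS2 censoring without declaring it, which matters for subjects with survival-only contacts

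*SAP*

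**What the plan says.** **Protocol.** Section 9.7.1.6.2 says that living subjects with no observed second progression "will be censored at the last time they are known to be alive and without a second objective disease progression". The synopsis (Analysis of Secondary Endpoints) gives the same two-part rule: such subjects "will be censored at the last time they are known to be alive and without a second objective PD". Section 9.7.1.1.2 adds: "Censoring rules for PFS2 will be defined in the SAP". The synopsis and Section 9.5.1.2.2 repeat that delegation.

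**SAP.** Under Section 8.4, if there is no second progression after a new anticancer treatment starts and no death, "the subject will be censored on the date last known to be alive". Second progression is established "solely based on the investigator-provided information on the Survival Status eCRF". Section 7 opens with "This SAP focuses on the analyses for the 2-arm design of the study". It then lists the analysis set for biomarker tables, the dropping of duration of clinical benefit, and the regrouping of QTc categories. PFS2 censoring is not listed.

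**Follow-up.** Protocol Section 9.1.2 provides 12-weekly follow-up for survival, PFS2 and anticancer treatment, but qualifies it: "unless this information is not allowed to be provided due to confidentiality". Section 9.5.1.2.2, Table 7 footnote v and SAP Section 3.2 carry the same exception. Protocol Section 9.3.3 keeps all subjects in survival follow-up until death, withdrawal of consent or the primary data cutoff.

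**The concern.** The SAP sentence drops half of the protocol's rule. What is left is a survival date, the same quantity that Section 8.4 uses to censor OS. SAP Table 4, by contrast, censors PFS at the last adequate radiologic assessment, that is, where disease status was last established.

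For a subject who is still contacted for survival but whose next-line course is not reported, no second progression can be recorded. Under the SAP rule the subject stays in the PFS2 risk set, event-free, up to the last survival contact.

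SAP Section 5.4.2 gives PFS2 the full PFS analysis: a stratified log-rank test at 0.05, a Cox hazard ratio, Kaplan-Meier quartiles, and rates at 6, 12, 18 and 24 months. All of these use the censoring date. An undeclared difference also leaves a reader of the protocol expecting a different estimate from the one that will be reported.

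**Working it through.** The documents state no PFS2 event count, power or effect size, so there is no figure of the plan's own to reproduce. The check is a comparison of texts, followed by an illustration of size.

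**1. The two rules side by side**

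| Source | Alive on the censoring date | Free of second progression on the censoring date |
|---|---|---|
| Protocol synopsis | required | required |
| Protocol 9.7.1.6.2 | required | required |
| SAP 8.4 | required | not mentioned |

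**2. When the dates differ.** Take each follow-up contact in turn.
- Alive, no second progression: both rules move the censoring date to this contact.
- Second progression or death: an event under both rules.
- Alive, progression status not reported: the SAP rule moves the date forward; the protocol rule leaves it at the last contact of the first kind.

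The extra event-free time is therefore (last date known alive) − (last date known alive and free of second progression). It is zero unless contacts of the third kind occur. The confidentiality exception, combined with continuing survival follow-up, makes them possible. So may telephone or email follow-up, which Table 7 footnote v allows.

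**3. Direction.** The Kaplan-Meier estimate is S(t) = ∏(1 − d/n) over event times. In the extra interval the subject counts in n, but a second progression cannot enter d; only death can. Each d/n is too small, so the curve moves up.

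**4. Illustration of size.** Inputs:
- Median time to first progression 18.3 months: Study 303, lenvatinib arm, Protocol Section 7.1.
- Cutoff uniform between 5.5 and 42 months after randomization. The lower end is 24 weeks (168 / 30.4375 = 5.5 months); the upper end is from Duration of Treatment in the synopsis.
- Assumed: exponential times; median 8 months (range 4 to 12) from first to second progression; median 12 months from second progression to death; a share q of subjects who progress before cutoff followed for survival only thereafter.

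Rates are ln 2 / median: 0.0379, 0.0866 and 0.0578 per month for medians of 18.3, 8 and 12 months. For a survival-only subject, death before cutoff is an event under both rules. Otherwise the SAP rule censors at cutoff and the protocol rule at first progression. All other subjects have time min(second progression, cutoff). Each scenario simulates 400,000 subjects.

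| First-to-second progression median | q | Full information | SAP rule | Protocol rule | SAP − protocol |
|---|---|---|---|---|---|
| 8 | 0 | 30.8 | 30.8 | 30.8 | 0 |
| 8 | 10% | 30.7 | 32.3 | 31.4 | 0.9 |
| 8 | 20% | 30.8 | 34.1 | 32.1 | 2.0 |
| 8 | 30% | 30.7 | 35.7 | 32.8 | 2.9 |
| 4 | 20% | 24.6 | 27.8 | 26.6 | 1.2 |
| 12 | 20% | 36.2 | 39.7 | 36.9 | 2.8 |

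The last four columns are in months; the three before the difference are median PFS2. The protocol-rule column assumes that knowledge stops at first progression. Second progression is defined as occurring on next-line therapy, so a subject may be known free of it until that therapy starts. A later date would narrow the gap.

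**5. Between arms.** With the 8-month assumption, the crude event rate (events / total time) relative to full information is 0.932 (SAP) and 0.957 (protocol) at q = 10%, and 0.867 and 0.913 at q = 20%. If two arms have the same true times and the same q, the rate ratio is 1 under either rule. With q = 20% in one arm and 10% in the other, it is 0.867 / 0.932 = 0.930 under the SAP rule and 0.913 / 0.957 = 0.954 under the protocol rule.

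**The case against.** The strongest reply is that the protocol hands this rule to the SAP, in three places. That stands: a reader might infer that the SAP overrides the protocol without authority, and the delegation rules this out. But the protocol also states a rule, so the two texts still conflict. Section 7 of the SAP records changes as small as the QTc categories, so this one belongs there too.

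Second, survival and PFS2 share the same 12-weekly contact, and second progression is read from the survival form. Where the form records both, the SAP sentence gives the same date as the protocol. That stands, and it limits the point to survival-only contacts.

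Third, a reader might infer from the missing cutoff limit, which the OS rule has, that PFS2 time beyond the data cutoff would be counted. The documents do not support this: Protocol Section 9.7 bases all analyses on the primary data cutoff, and off-treatment PFS2 and survival follow-up end there. Stating the limit is a clarification only.

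Fourth, the protocol rule is not unbiased either. In the illustration it too lies above full information (32.1 against 30.8 months at q = 20%), partly because an unseen second progression is counted only at death. That stands: restoring the rule reduces the bias but does not remove it.

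**Conclusion.** The point holds as an undeclared difference between SAP and protocol on the censoring date of a secondary endpoint. The text mismatch is certain. The consequence is conditional: PFS2 curves shift upward to the extent that subjects have survival-only contacts after their progression status was last known. On the assumed inputs, the SAP rule adds 0.9 to 2.9 months to the median over the protocol rule for q from 10% to 30%, and nothing at q = 0. The share q is an assumption; the documents give no count.

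Two stronger readings go too far. One is that PFS2 is inflated for censored subjects in general; it is not, because the dates coincide wherever both statuses are recorded together. The other is that the hazard ratio is biased; that arises mainly if survival-only follow-up differs between 18 mg and 24 mg, and nothing in the documents shows that it does. The ORR at 24 weeks and the Grade 3 or higher TEAE rate do not use this rule and are unaffected.

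**What to change.** In SAP Section 8.4, censor a living subject with no recorded second progression at the last date on which the subject was documented both alive and without second objective progression. State, for clarity, that this date is no later than the data cutoff.

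If the sponsor prefers the present SAP rule, declare and justify it in Section 7 and run the protocol's rule as a sensitivity analysis for PFS2.

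The first option costs one sentence in the SAP, and PFS2 medians may come out slightly shorter. The second costs an entry in Section 7 and a repeat of the PFS2 analysis.
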